12.6 Visit 5: Clinical Follow-Up 18 Months

18 months \pm 4 weeks post the last breath test performed a phone / in-person visit will be conducted in order to assess major clinical events (i.e. Death, liver transplant, liver decompensation events including: ascites, hepatic encephalopathy, variceal bleeding, hepato-renal syndrome, spontaneous bacterial peritonitis). In addition, the patient's clinical records will be reviewed.

NOTE: Patients undergoing intervention for NASH / NAFLD, including both approved and experimental approaches prior to the defined time points will be terminated hence will not be evaluated for this endpoint.

Exalenz Bioscience Ltd.	Last update on: May1, 2016
Study Title: Clinical Study of the BreathID [®] System to train the algorithm for the ¹³ C-Octanoate Breath Test with or without the ¹³ C-Methacetin Breath Test (OBT and MBT respectively) for correlation with histological findings of Non-Alcoholic Fatty Liver Disease (NAFLD)	Protocol No.: NASH-EX-1114
	Version: 1f
Document N^o: CSD00080	Page 41 of 61

12.7 Visit 6: Clinical Follow-Up 36 Months

36 months \pm 8 weeks post the last breath test performed a phone / in-person visit will be conducted in order to assess major clinical events (i.e. Death, liver transplant, liver decompensation events including: ascites, hepatic encephalopathy, variceal bleeding, hepato-renal syndrome, spontaneous bacterial peritonitis). In addition, the patient's clinical records will be reviewed.

NOTE: Patients undergoing intervention for NASH / NAFLD, including both approved and experimental approaches prior to the defined time points will be terminated hence will not be evaluated for this endpoint.

NOTE: Any AEs reported that are possibly or probably related to the use of the product or related to the procedure within 36 months post last breath test performed or until subject termination will be followed until resolution and if laboratory work is done secondary to AEs and found abnormal, these tests will be followed until normalization or stabilization.

13 ETHICS & REGULATORY CONSIDERATIONS

13.1 Ethics & Regulatory Approvals

The study will be conducted in both the United States of America and Europe. As such, regulatory bodies that are relevant for all countries will be mentioned in this section.

The study will be conducted in compliance with the principles of the Declaration of Helsinki (1996), the principles of GCP and in accordance with all applicable regulatory requirements.

This protocol and related documents will be submitted for review to all relevant ethics committees delegated to approve the study at their respective sites. Any amendment to the protocol may be proposed by the principal investigator. The amendment must be submitted to the Sponsor and, when approved to the relevant institutional review board (IRB) or ethics committee (EC). When applicable, the implementation of the amendment will take place only once approved by the appropriate ethics committee.

Annual progress and safety reports and a final report at conclusion of the study will be submitted by Exalenz Bioscience (or on behalf of the Sponsor) to the applicable regulatory bodies within the timelines defined in the Regulations.

Exalenz Bioscience Ltd.	Last update on: May1, 2016
Study Title: Clinical Study of the BreathID [®] System to train the algorithm for the ¹³ C-Octanoate Breath Test with or without the ¹³ C-Methacetin Breath Test (OBT and MBT respectively) for correlation with histological findings of Non-Alcoholic Fatty Liver Disease (NAFLD)	Protocol No.: NASH-EX-1114
	Version: 1f
Document N^o: CSD00080	Page 42 of 61

14 INVESTIGATOR RESPONSIBILITIES

The investigator is responsible for ensuring that the clinical study is performed in accordance with the protocol, current ICH guidelines on GCP, and applicable regulatory requirements. GCP is an international ethical and scientific quality standard for designing, conducting, recording, and reporting studies that involve the participation of human subjects. Compliance with this standard provides public assurance that the rights, safety, and well-being of study subjects are protected, consistent with the principles that originated in the Declaration of Helsinki, and that the clinical study data are credible.

The investigational devices will bear an identification number and their accountability will be filed in the Investigator's Study File. Study supplies logged in will be kept by the investigator or the delegated persons in a secure place. All supplies (device, substrate and cannulae) will be used for this study only. After completion of the study, the device, drug and all unused accessories must be returned to Exalenz Bioscience Ltd. as per their request or alternatively, destroyed according to local regulations after receiving explicit authorization by Exalenz to do so and provide Exalenz with a confirmation.

The Principal Investigator will act as custodian for the study data. Patient data will be anonymized and all the anonymized data will be stored on a password protected computer. All data will be compliant with CFR and GCP.

14.1 Investigational Product Handling

The Investigator and Research Pharmacist (if relevant) will be provided with *Investigational Product Handling Guidelines* that will provide details regarding the packaging and labeling requirements, receipt of investigational product, dispensing and accountability procedures, preparation instructions, storage and stability of Investigational product, disposition of Investigational product, with the following forms required: Proof of Receipt Form, Temperature Logs, Accountability Logs, Investigational Product and Material Transfer/Disposition Form and Pharmacy Staff Identification Log (if applicable).

Local forms may be authorized for use after being approved by the Sponsor or his assigned representative.

Exalenz Bioscience Ltd.	Last update on: May1, 2016
Study Title: Clinical Study of the BreathID [®] System to train the algorithm for the ¹³ C-Octanoate Breath Test with or without the ¹³ C-Methacetin Breath Test (OBT and MBT respectively) for correlation with histological findings of Non-Alcoholic Fatty Liver Disease (NAFLD)	Protocol No.: NASH-EX-1114
	Version: 1f
Document N^o: CSD00080	Page 43 of 61

14.2 Investigational Product Accountability

The Investigator and Study Pharmacist (if relevant) are responsible for ensuring that all study supplies received at the site are inventoried and accounted for throughout the study. The dispensing of study substrate to the subject must be documented in the respective accountability form. The study Investigational Product must be handled in strict accordance with the protocol and the container label and will be stored in a limited access area or in a locked cabinet under appropriate environmental conditions. Unused study materials must be available for verification by the sponsor's site monitor during on-site monitoring. The destruction of unused study materials (both, expired or unexpired) will be documented on the return/disposition form. The Sponsor will authorize to destroy excess supplies on site according to local policy. In this case, before proceeding, the site must seek authorization from the Sponsor using the Return/destruction form and this must also be documented on the Study Supply Return Form.

Study substrate should be dispensed under the supervision of the investigator, a qualified member of the investigational staff, or by hospital clinical pharmacist.

15 SAFETY CONSIDERATIONS

15.1 Adverse Event Definitions

An adverse event (AE) is any undesirable or unintentional event that occurs during use of the study medical device or drug, whether or not considered related to the investigational product; this includes clinically significant changes in laboratory values related to acetaminophen exposure. As this study is not therapeutic in nature, there will be no therapeutic failures to report. Regardless of severity or relationship to the study investigational product, these are recorded in the patient's CRF, all adverse events occurring during the time period when study investigational product is being administered. Associated with the use of the investigational product is defined as a reasonable possibility that the event may have been caused by the medical device or drug.

NOTE: Any AEs reported that are possibly or probably related to the use of the product or related to the procedure within 36 months post last breath test performed or until subject termination will be recorded and followed until resolution and if laboratory work is done secondary to AEs and found abnormal, these tests will be followed until normalization or stabilization.

Serious Adverse Event (SAE) and Suspected Unexpected Serious Adverse Reactions (SUSAR)

Exalenz Bioscience Ltd.	Last update on: May1, 2016
Study Title: Clinical Study of the BreathID [®] System to train the algorithm for the ¹³ C-Octanoate Breath Test with or without the ¹³ C-Methacetin Breath Test (OBT and MBT respectively) for correlation with histological findings of Non-Alcoholic Fatty Liver Disease (NAFLD)	Protocol No.: NASH-EX-1114
	Version: 1f
Document N^o: CSD00080	Page 44 of 61

A serious adverse event (SAE) is an event that is either:

- a) fatal
- b) life-threatening
- c) results in persistent or significant disability/incapacity
- d) requires or prolongs inpatient hospitalization
- e) is a congenital anomaly or birth defect.

A Suspected Unexpected Serious Adverse Reactions (SUSAR) is an SAE, for which the nature or severity is not consistent with the expected outcomes of the treatment being offered.

Life threatening is defined as an event in which the patient is at risk of death at the time of the event. It does not refer to an event that hypothetically might have cause death if it was more severe. Disability is defined as a substantial disruption of a person's ability to conduct normal life functions. An unexpected adverse event is one that has not been previously observed, or one that is of a specificity or severity not consistent with the current investigator brochure.

When an adverse event occurs, record the following information and assessments in the adverse event section of the CRF:

- The signs, symptoms, or diagnosis of the event
- The date and time of onset of the event using the 24 hour clock where midnight is 00:00 and noon is 12:00
- The adverse event severity using the criteria outlined below
- The relationship of the event to the study medical device as outlined below
- Describe any action taken regarding study medical device disposition
- List any required therapy, medication, treatment, or diagnostic procedure.

15.2 Relationship to Study medical device

Use the following definitions to assess the relationship between an adverse event and the study medical device.

- Not Related:

Exalenz Bioscience Ltd.	Last update on: May1, 2016
Study Title: Clinical Study of the BreathID [®] System to train the algorithm for the ¹³ C-Octanoate Breath Test with or without the ¹³ C-Methacetin Breath Test (OBT and MBT respectively) for correlation with histological findings of Non-Alcoholic Fatty Liver Disease (NAFLD)	Protocol No.: NASH-EX-1114
	Version: 1f
Document N^o: CSD00080	Page 45 of 61

The event is clearly related to other factors such as the patient's clinical state, therapeutic interventions or concomitant drugs.

- Remotely Related:

The event was most likely produced by other factors such as the patient's clinical state, therapeutic interventions or concomitant drugs and does not follow a known response pattern to the study medical device.

- Possibly Related:

The event has a reasonable temporal relationship to study medical device administration and follows a known response pattern to the study medical device. However, a potential alternate etiology may be responsible for the event. The effect of medical device withdrawal is unclear. Re-challenge information is unclear or lacking.

- Probably Related:

The event follows a reasonable temporal sequence from the time of medical device administration and follows a known response pattern to the study medical device and cannot be reasonably explained by other factors. There is a reasonable response to withdrawal of the medical device. Re-challenge information is not available or advisable.

- Related:

The event follows a temporal sequence from the time of medical device administration and follows a known response pattern to the study medical device and either occurs immediately following study medical device administration, or improves on stopping the medical device, or reappears on repeat exposure.

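### Section 15.2 requires a known response pattern for every grade from Possibly Related upward, so a new type of reaction with plausible timing and no clear or most likely other cause fits none of the five grades

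*Combined protocol and SAP*

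**What the plan says.** Section 15.1 lists what the site enters on the CRF for each adverse event, including "The relationship of the event to the study medical device as outlined below". Section 15.2 then instructs: "Use the following definitions to assess the relationship between an adverse event and the study medical device". Its five grades set these conditions:

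- *Not Related*: "The event is clearly related to other factors".
- *Remotely Related*: "The event was most likely produced by other factors", and the event shows no known response pattern.
- *Possibly Related*: "The event has a reasonable temporal relationship to study medical device administration and follows a known response pattern to the study medical device". It adds that another cause may be responsible.
- *Probably Related*: plausible timing, and the event "follows a known response pattern to the study medical device and cannot be reasonably explained by other factors". A further sentence speaks of a response to withdrawal.
- *Related*: the event has a temporal sequence and "follows a known response pattern to the study medical device and either occurs immediately following study medical device administration", or improves on stopping, or returns on re-exposure.

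There is no unknown or unassessable grade and no default rule.

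The same chapter foresees new reactions: "An unexpected adverse event is one that has not been previously observed". Under 15.4, the written report on a serious unexpected event must assess its relationship to the device. Section 9.2 expects no breath-test related events, and 5.2.2.1 and 5.2.3.2 describe no observed reaction to either substrate.

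**The concern.** The pattern condition is joined to the timing condition by 'and' in all three upper grades. A first case of a new reaction cannot meet it, because nobody has yet described the pattern. Unless another cause is clear or most likely, the two lower grades are closed as well.

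Three things use relatedness. Section 11.7.4 reports the rate of related AEs with an exact 95% interval and tabulates AEs by relationship. Sections 9.5 and 15.1 provide follow-up to resolution for AEs possibly or probably related to the product. Section 15.4 needs the assessment in the report on a serious unexpected event. An event without a grade can be missing from the first two, or each site may improvise its own answer. In a study that expects no related events, the label on a first case is the information most worth getting right.

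**Working it through.** The plan gives no figure to reproduce, so the check takes the five definitions as logical conditions.

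**Inputs.** Timing is taken as plausible. The event's pattern is known or new (2 states). The other cause is clear, most likely, possible or absent (4 states). That gives 2 × 4 = 8 situations. A 'feature' means immediate onset, improvement on stopping, or recurrence on re-exposure. The withdrawal sentence in *Probably Related* is taken as met. The last column uses the wording given under the fix.

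| Pattern | Other cause | Current text | Proposed text |
|---|---|---|---|
| known | clear | Not Related; literally also Possibly, and Related with a feature | Not Related |
| known | most likely | Possibly; also Related with a feature | Possibly |
| known | possible | Possibly; also Related with a feature | Possibly |
| known | none | Probably; also Related with a feature | Probably, or Related with a feature |
| new | clear | Not Related | Not Related |
| new | most likely | Remotely Related | Remotely Related |
| new | possible | **no grade** | Possibly |
| new | none | **no grade** | Probably, or Related with a feature |

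Under the current text 2 of 8 situations have no grade. Splitting each by presence or absence of a feature gives 4 combinations, and all 4 meet none of the five grades. An immediate or recurring reaction still fails *Related*, because the list of features is added to the pattern condition and does not replace it. Under the proposed text 0 of 8 lack a grade and each has one, with *Related* as the upper step of *Probably*. This assumes that plausible timing with no more than a possible alternative leaves a reasonable possibility of causation.

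The check is confined to plausible timing. With implausible timing the same coding leaves 10 of 16 combinations without a grade. Those are outside this point, and the fix does not address them.

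**Effect on the related-AE rate.** Exact (Clopper-Pearson) 95% intervals, with assumed event counts. For zero events the upper limit is 1 − 0.025^(1/n). The sample sizes of 200 and 400 are from 11.5.

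| Events / n | Rate | Exact 95% CI |
|---|---|---|
| 0 / 200 | 0% | 0 to 1.83% |
| 1 / 200 | 0.5% | 0.01 to 2.75% |
| 2 / 200 | 1.0% | 0.12 to 3.57% |
| 0 / 400 | 0% | 0 to 0.92% |
| 1 / 400 | 0.25% | 0.006 to 1.385% |

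One ungraded event moves the report from the second row to the first, or from the fifth to the fourth. If one site grades such an event and another does not, two events read as one.

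**How many events to expect.** The documents give no rate for new reactions. Section 5.2.3.2 reports no related events among 1,466 + 74 = 1,540 people given methacetin with this device. The upper limit is 1 − 0.025^(1/1540) = 0.239%, or at most about 0.00239 × 200 = 0.48 events in 200 and 0.00239 × 400 = 0.96 in 400. This bounds all related methacetin events, of which new-pattern events are only a part. No comparable denominator is given for octanoate.

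**The case against.** **The clauses are read unevenly.** The check enforces the pattern clause and takes the withdrawal sentence as met. If that sentence were enforced for single-dose substrates, a known-pattern event with no other cause and no feature would also lose its grade, making 3 of 8. If all these sentences are only guides to judgement, the gap narrows. This stands as a limit on the count. It does not remove the gap, because no reading of the words as written gives a new-pattern event one of the upper grades. Judgement that departs from the definitions can also differ between sites.

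**Section 15.1 already has a looser standard.** It defines association with the product as a reasonable possibility of causation, with no pattern test, and 11.7.4 does not say which grades count as related. The related-AE rate might therefore be built on 15.1. That is fair, and it makes the effect on the rate a possibility and not a certainty. But 15.1 ties its standard to no grade, and the CRF entry is directed to the 15.2 definitions.

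**Known patterns may be broader than they look.** A reader might infer that any true reaction would be ungradable, since none has been reported. The documents do not support that. Hypersensitivity (10.2), acetaminophen-related laboratory changes (15.1), the toxicities listed in 15.5 and anything in the Investigator Brochure may count as known.

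**Safety oversight is largely independent of the grade.** A reader might infer that a dangerous reaction could go unseen or escape the stopping rule. The documents do not support that either. All AEs are recorded and reported to authorities, serious unexpected ones go to the medical monitor and the EC or IRB (15.4), and withdrawal for CTCAE Grade 3 or higher does not depend on attribution to the drug (10.6). The stopping rule for a Grade 4 event does need attribution to a breath test, but it does not cite the 15.2 grades. An ungraded event also stays in the overall incidence and severity tables, and an event related to the procedure has its own route to follow-up (9.5).

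**The word 'device'.** It might be read as leaving the substrates out of 15.2. Section 5.2.1 includes the substrate in the BreathID System, so this is not an error.

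**Conclusion.** The gap is real on the plain wording. A reaction of a new type, with plausible timing and no clear or most likely other cause, fits none of the five grades, and nothing elsewhere in the protocol assigns it one. The wording itself is not in doubt. The practical reach is uncertain, because it depends on which patterns the Investigator Brochure lists and on which grades the analysis counts as related.

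The effect is on how rare first cases are classified and followed up. The intervals with and without one such event overlap widely, the event counts are assumed, and the safety analysis is descriptive. What can change is whether the report says 'no related events' or 'one related event'. That is worth correcting because the repair is cheap. It does not call for a change in design or sample size.

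**What to change.** In the three upper grades, treat a known response pattern as supporting evidence and not as a requirement, and word the grades so that they exclude one another:

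- *Not Related*: unchanged (another cause is clear).
- *Remotely Related*: unchanged (another cause is most likely and there is no known pattern).
- *Possibly Related*: plausible timing and a reasonable possibility of causation, with another cause possible but not most likely, or most likely where the event follows a known pattern.
- *Probably Related*: plausible timing and no reasonable explanation by other factors. Response to withdrawal is considered only where applicable, because each substrate is given as a single dose.
- *Related*: as *Probably Related*, plus immediate onset, improvement on stopping, or recurrence on re-exposure. The higher grade applies when both are met.

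The limit on *Possibly Related* is needed. Without it, a new-pattern event with a most likely other cause could meet both *Remotely* and *Possibly Related*.

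The cost is a wording amendment to 15.2 and the matching CRF guidance, approved by the sponsor and submitted to the IRBs and ECs (13.1). No extra visits or data are needed. The related-AE rate may come out slightly higher. Some known-pattern events with immediate onset and another plausible cause would move from *Related* to *Possibly Related*, because *Related* at present has no condition on other causes.

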15.3 Adverse Event Severity

- Mild Adverse Events

A mild adverse event is one that the symptoms are barely noticeable to the patient. It does not influence performance, require drug treatment or prevent the patient from carrying on with normal life activities.

- Moderate Adverse Events

Exalenz Bioscience Ltd.	Last update on: May1, 2016
Study Title: Clinical Study of the BreathID [®] System to train the algorithm for the ¹³ C-Octanoate Breath Test with or without the ¹³ C-Methacetin Breath Test (OBT and MBT respectively) for correlation with histological findings of Non-Alcoholic Fatty Liver Disease (NAFLD)	Protocol No.: NASH-EX-1114
	Version: 1f
Document N^o: CSD00080	Page 46 of 61

A moderate adverse event is one that the symptoms make the patient uncomfortable and causes some impairment to normal life activities. Treatment for symptom(s) may be required.

- Severe Adverse Events

A severe adverse event is one that the symptoms cause severe discomforts to the patient and severely limits the patient's normal daily activities. Treatment for symptom(s) is given.

Note: Serious and severe are not synonymous. A serious adverse event must fulfill the requirements listed in the definition above.

